- The study pessary will be removed. The orientation of the study pessary inside the vagina will be noted prior to removal. Discomfort with removal will be recorded by VAS. The study pessary will be washed with anti-bacterial soap and tap water and inserted into a resealable bag along with its original packaging. The used study pessary should be returned to [name] office which is adjacent to the clinic space where the study is being conducted *[research purposes]*.
- The current pessary will be re-inserted, *[would be done anyway]* and pain will be recorded by VAS *[research purposes]*. The subject will give a global impression of study pessary comfort in comparison to current pessary *[research purposes]*.

Data Collected

After the subject provides consent, the subject's medical record will be abstracted for their medical history. The subject may be asked to clarify the medical record. Data to be collected includes:

Medical History

- Age
- BMI (kg/m^2)
 - ∘ <20
 - o 20**-**30
 - o >30
- Previous gynecologic surgeries
 - Hysterectomy
 - Prior prolapse surgery
 - Prior UI surgery

- Other gynecologic surgery
- Previous non-surgical prolapse treatment
 - Pelvic floor exercises
 - Pessary use
- Parity
 - No. of births
 - No. of vaginal births
- Estrogen status
 - Pre-menopausal
 - Post-menopausal
 - o HRT
- Concomitant disorders
 - Urinary Incontinence
 - Fecal Incontinence
 - Other
- Prolapse stage
- POP-Q measurements prior to pessary fitting

Outcomes

- Pessary retention and function
 - Retained, normal position
 - Comes out fully deployed before ambulation
 - Collapses and comes out before ambulation
 - Comes out during ambulation
 - Comes out when on toilet, attempting void
- Rotation during ambulation
- Distance from the leading edge of the pessary to hymen with Valsalva
 - Original pessary
 - Study pessary
- Discomfort with insertion and removal (VAS completed by subject)
 - Original pessary
 - Study pessary
- Difficulty with insertion and removal (5 point scale completed by provider)
 - Original pessary
 - Study pessary
- Global impression of comfort while using pessary (3 point scale completed by subject)
- Global impression of ease of use (5 point scale completed by provider)

See attached data collection forms. Forms will be filled out in ink and stored according to procedures outlined in "17.0 Data Management and Confidentiality."

Transition from Research Participation

At the conclusion of the study, each subject will have her current pessary replaced in her vagina, and she will be instructed to present for her next routinely scheduled follow up visit per her typical care.

7.0 Data and Specimen Banking

N/A

8.0 Sharing of Results with Subjects

The performance of the study pessary will be verbally shared with each subject who is interested at the time of the visit.

9.0 Study Timelines

It is anticipated that each participant will be involved in the study for approximately one hour. The study is designed to enroll 15 subjects presenting for routine pessary care to the Division of Female Pelvic Medicine and Reconstructive Pelvic Surgery at Dartmouth-Hitchcock Medical Center. This study site sees an average of 50 patients per month for routine pessary care of which 80% are using a ring style or Gellhorn pessary and would be eligible to participate. Assuming 1:8 patients who is eligible agrees to participate, it should take 3 months to recruit patients and complete this study.

10.0 Inclusion and Exclusion Criteria

Sex of Subjects

Pelvic organ prolapse (POP) is a disease which only affects females, most typically those who are post-menopausal. Males will not be recruited for this study.

Age of Subjects

Study participants will be at least 18 years old. Pelvic organ prolapse is primarily a disease of post-menopausal women and is therefore not relevant to the population of women less than 18 years old.

Racial and Ethnic Origin

Pelvic organ prolapse (POP) is a disease which only affects females, most typically those who are post-menopausal. Males will not be recruited for this study. This is an early feasibility study in which 15 subjects will be recruited from a clinical practice at Dartmouth-Hitchcock Medical Center, a tertiary care facility in Lebanon, NH. Eligible subjects will be screened for participation sequentially as they present for routine pessary care without excluding individuals based on race or ethnicity. 2018 US Census estimates for nearby Claremont, NH, which has similar demographics to Lebanon, demonstrates a population which is 97.6% White alone, 0.9% Black or African American alone, and

PROTOCOL TITLE: *Early Feasibility Prospective Open Label Study to Assess the Function of a Novel Pessary for the Non-Surgical Management of Pelvic Organ Prolapse*

0.4% Asian alone. 2.4% are Hispanic or Latino. The population recruited for this study would have similar characteristics.

Inclusion Criteria

- Women with Stage II pelvic organ prolapse or greater
- Current ring style or Gellhorn pessary users inclusive of sizes 1.5"-3.5"
- Capable of giving informed consent

Exclusion Criteria

- Pregnancy
- Deep vaginal erosion noted with removal of current pessary
- Presence of vesicovaginal fistula
- Presence of rectovaginal fistula
- Vaginal, rectal, or bladder tumor
- Inflammatory Bowel Disease
- Presence of open wound or tear near vagina or anus by exam prior to removal of current pessary
- Current vaginal or urinary infection requiring treatment
- Previous pelvic floor surgery in last 12 months
- Congenital malformation of bladder, rectum, or vagina
- Significant medical condition interfering with study participation (psychologic, neurologic, active drug/alcohol abuse, etc.)
- Planning pregnancy in next 6 months

Vulnerable Subjects

Subjects will not be recruited to this study if they are identified as a member of a vulnerable population.

11.0 Vulnerable Populations

N/A

12.0 Local Number of Subjects

15 subjects will be recruited for this study. Typical early feasibility studies for medical devices include 5-15 subjects. The upper bound was selected due to the variability of the presentation of prolapse (apical, anterior, or posterior, as well as degree of severity) to evaluate performance of the Reia Vaginal Pessary across a broader range of clinical presentations.

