5.0 Study Intervention/Investigational Agent

Please see attached document for device description and non-significant risk rationale.

6.0 **Procedures Involved**

Methods

Current users of existing marketed pessaries typically present to their providers every 3-4 months so that their pessary can be removed and cleaned and their vagina can be inspected for erosion caused by their device. Fifteen subjects will be recruited for this study from a panel of established patients who present for this routine care of their ring style or Gellhorn pessary to a clinical practice at the Dartmouth-Hitchcock Clinic specializing in Female Pelvic Medicine and Reconstructive Surgery (FPMRS). Inclusion will be based on pre-defined criteria outlined in "10.0 Inclusion and Exclusion Criteria." There will not be discrimination based on race or ethnicity. It is anticipated that most participants will be post-menopausal as this reflects the demographic of women who suffer from this disorder. Treatment intervention will be non-blinded to the subject and investigator and will occur in a single visit. Each subject will receive the study pessary and wear it in a controlled environment for less than 1 hour. Assessment of the study pessary's performance to support the subject's prolapse will be determined by measuring the baseline distance between the leading edge of each subject's current pessary to the hymen and comparing that to the measured distance between the leading edge of the study pessary to the hymen, as well as by observing the ability of the study pessary to be retained with simulated activities of daily life such as walking and toileting. Secondary outcomes of subject comfort with insertion, use, and removal of the study pessary will be measured.

The study pessary is the only device which will be used in this trial, though the subject will arrive for her visit and leave with her current pessary. There will be no placebo devices placed. The study pessary is not cleared by the FDA, and a rationale is provided for a non-significant risk device claim in the attached documents. This trial was devised so that it could take place at the time in which subjects present for usual care of their current pessary, and the procedures are consistent with the standard of care at Dartmouth-Hitchcock Medical Center, the site of the study.

Study Procedures

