14.0 Withdrawal of Subjects

Reasons for a subject to be withdrawn from the research study include:

- The subject is found to have a condition which does not allow participation in the research, such as a finding upon physical examination that excludes them from the study.
- The subject has a reaction that requires immediate removal of the research pessary.

If a subject is removed, already collected data may not be removed from the study database and will be handled with the same protocol as research data. The subject will receive the usual ongoing care for their pessary.

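### The synopsis gives a sample size of 15-20 while the rest of the protocol and the SAP give 15, and the SAP's 4-of-15 rule narrowly misses its stated p < .05

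*Protocol*

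**What the plan says.** **Sample size.** The Sample Size row of the synopsis (protocol section 1.0) reads 15-20. Everywhere else the number is 15:

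- Section 6.0, Methods: "Fifteen subjects will be recruited for this study from a panel of established patients".
- Section 9.0: "The study is designed to enroll 15 subjects presenting for routine pessary care".
- Section 10.0: "This is an early feasibility study in which 15 subjects will be recruited from a clinical practice".
- Section 12.0, the section that justifies the planned size: "15 subjects will be recruited for this study. Typical early feasibility studies for medical devices include 5-15 subjects. The upper bound was selected", the reason given being the variety of prolapse presentations.
- Section 18.0 cites 15 subjects, one visit each and a 3-month recruitment period among its reasons for having no formal monitoring committee.
- Section 25.0 has fifteen participants.
- The SAP, Statistical Design and Power, sets out to discuss the choice of 15.

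**Timeline.** Sections 9.0 and 25.0 assume 50 pessary-care patients per month, 80% of them eligible and 1 in 8 of those agreeing. Section 9.0 concludes that "it should take 3 months to recruit patients and complete this study".

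**SAP rule.** The SAP takes 21 refits among 57 women from a published Gellhorn series (37%), with an exact binomial 95% interval of 24% to 51%. It uses the upper limit, .51, as the null failure rate. It states that 4 or fewer refits out of 15 would reject that null at p < .05, and that power is at least .81 if the true rate is 21% or lower.

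**The concern.** A planned sample size should have one value, or a range with a stated purpose. Here the summary allows up to a third more subjects than the sections that justify, schedule and analyse the study. The device is not FDA-cleared, so the number of women exposed to it should not differ between the synopsis and the body. If 20 were really intended, the size rationale, the timeline and the SAP's cut-off and power would all describe a different study.

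The SAP's rule raises a second question that does not depend on the first. With only 15 subjects the exact binomial distribution moves in large steps, so a cut-off described as giving p < .05 needs checking against the exact tail probability.

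**Working it through.** **1. Does each supporting figure fit 15 or 20?**

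- Rationale: section 12.0 picks the upper bound of 5-15. That bound is 15, and 20 lies outside the range.
- Accrual: 50 × 0.80 ÷ 8 = 5 per month. 15 ÷ 5 = 3 months, which reproduces section 9.0. 20 ÷ 5 = 4 months.
- SAP: the rule and the power are stated for 15 only.

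**2. Reproducing the SAP's figures at N = 15.** X is the number of refits, binomial (15, π).

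- Exact 95% interval for 21/57: .2445 to .5066. This matches 24% to 51%.
- Power of the 4-or-fewer rule at π = .21: P(X ≤ 4) = .0291 + .1162 + .2162 + .2490 + .1986 = .809. This matches .81.
- Level of the same rule at π = .51: P(X ≤ 4) = .0000 + .0004 + .0026 + .0116 + .0361 = .0506 (terms rounded). This is not below .05.
- Rounding the null does not explain the gap. With the unrounded limit .5066 the probability is .0535, which is further from .05.
- An uncorrected normal approximation would give z = (4 − 15 × .51)/√(15 × .51 × .49) = −3.65/1.936 = −1.885, p = .030. Mid-p gives about .033. The SAP mentions neither; the one method it names, for its interval, is exact.
- The largest cut-off with exact p < .05 is 3: P(X ≤ 3 | .51) = .0145, with power P(X ≤ 3 | .21) = .61.

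**3. What the SAP would need for each N in the range.** The cut-off c is the largest with P(X ≤ c | N, .51) < .05; power is P(X ≤ c | N, .21).

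| N | c | exact p | power at 21% |
|---|---|---|---|
| 15 | 3 | .0145 | .61 |
| 16 | 4 | .0322 | .77 |
| 17 | 4 | .0202 | .72 |
| 18 | 5 | .0402 | .84 |
| 19 | 5 | .0261 | .81 |
| 20 | 6 | .0480 | .89 |

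The cut-off cannot simply be carried over. Keeping 4 or fewer at N = 20 would give a level of .0046 and power of .586.

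**The case against.** **On the sample size.** One cell disagrees with six protocol sections and the SAP, and the dedicated section gives 15 with a reason. A careful reader would take 15 as operative and the cell as an uncorrected entry. That stands, and it limits the weight of the point, but the cell still contradicts the rest.

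A reader might go further and infer that the documents leave open whether 15 counts enrolled subjects, or that nobody could tell when enrolment stops. The text does not support this. Section 9.0 speaks of enrolling 15, and sections 6.0, 10.0 and 12.0 of recruiting 15.

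A reader might also infer that 15-20 is an allowance for replacing women excluded at examination. One exclusion can be found only at that stage ("Deep vaginal erosion noted with removal of current pessary"), and section 14.0 provides for withdrawal on grounds "such as a finding upon physical examination that excludes them from the study", adding that "already collected data may not be removed from the study database". But no passage links the range to such losses or gives a loss rate. Section 22.0 has eligibility confirmed before the consent process starts, and section 18.0 expects incidental findings to be unlikely. Nor is the retention denominator seriously in doubt, since a woman who never receives the study pessary has no retained or expelled result.

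**On the SAP rule.** The excess over .05 is .0006, the exact method is named for the interval and not expressly for the test, and moving to 3 of 15 would cut power from .81 to .61. All of this is fair. It argues for restating the level and against treating the rule as unsound. It does not make .0506 less than .05.

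**Conclusion.** The point holds on two counts.

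First, the synopsis figure of 15-20 contradicts 15 in sections 6.0, 9.0, 10.0, 12.0, 18.0 and 25.0 and in the SAP, without explanation. The size rationale, the 3-month timeline and the SAP calculation belong to 15 alone.

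Second, and whichever N is kept, the SAP's 4-of-15 rule has an exact one-sided level of .0506 against .51, while its power of .81 is right. This rests on an exact one-sided test at the null of .51 that the SAP states. The SAP does not give the sidedness, but its null is directional.

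The stakes are modest. Refit rate is not among the endpoints in section 4.0, and the SAP itself says that formal procedures and power are not the main focus of an early feasibility trial. It would also be wrong to infer that a larger N harms the test: with cut-offs re-derived to keep the exact p below .05, power at 16 to 20 is .72 to .89, against .61 at 15.

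**What to change.** **Sample size.** Change the synopsis cell to 15. This costs one edit. Section 12.0 could also gain a sentence on whether women excluded at examination are replaced. That is optional; without replacement, any such exclusion leaves fewer than 15 with study-pessary results.

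If the range is intended, state its purpose, align sections 6.0, 9.0, 10.0, 12.0, 18.0 and 25.0, extend the timeline to 4 months for 20, and put the cut-off and power for each N from 16 to 20 into the SAP as tabulated above. This costs edits to six sections, up to one more month of recruitment, and up to five more gift cards (5 × $100 = $500).

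**SAP.** In either case correct the sentence for N = 15. One option is to keep 4 of 15 and give the level as about .051 with power .81. If a level strictly below .05 is wanted, the other is to use 3 of 15 with p = .0145 and power .61. Each takes one sentence; the second gives up .20 of power. Given the SAP's descriptive purpose, restating the level is the lighter change.

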13.0 Recruitment Methods

Method of Subject Identification and Recruitment

Subjects will be recruited from a panel of established patients in a clinical practice specializing in FPMRS at the Dartmouth-Hitchcock Clinic. There will be no advertisements. Screening for potential subjects during a given week of care will be

PROTOCOL TITLE: *Early Feasibility Prospective Open Label Study to Assess the Function of a Novel Pessary for the Non-Surgical Management of Pelvic Organ Prolapse*

based on scheduled visit type, duration, and type of pessary currently in use. Prospective subjects will have their name, medical record number, and telephone number recorded on a handwritten list with pen and paper. With the list complied, subjects will be contacted by telephone, and using the submitted phone script (see attached document), their interest in participation will be gauged. The list will be shredded after all potential subjects are contacted. If they demonstrate a preliminary interest, they will be scheduled for the appropriate amount of time to complete consent in-person and enter the study as they present for their pessary care visit. Additionally, the recruiter will offer to mail prospective subjects a copy of the consent form to review ahead of their appointment. Preferred mailing addresses will be collected over the telephone and handwritten directly on the mailing envelope and not copied elsewhere.

Payment for Participation

Participants will be offered a \$100 gift card in compensation for the time due to participation that is in excess of the typical time required for routine pessary care.

Alternatives to Participation

If the patient elects not to participate in the study, they will proceed with their usual appointment and care.

14.0 Withdrawal of Subjects

Reasons for a subject to be withdrawn from the research study include:

- The subject is found to have a condition which does not allow participation in the research, such as a finding upon physical examination that excludes them from the study.
- The subject has a reaction that requires immediate removal of the research pessary.

If a subject is removed, already collected data may not be removed from the study database and will be handled with the same protocol as research data. The subject will receive the usual ongoing care for their pessary.

15.0 Risks to Subjects

This study will involve greater than minimal risk. The subject could experience minor discomfort with insertion and deployment of the study pessary, while she is being asked to Valsalva, or if the study pessary is expelled with Valsalva. There could be minor abrasion of the vaginal epithelium with the study pessary upon insertion or removal or disruption of the perineal epithelium. The risk of these events occurring should be lower than them occurring during usual care because the study pessary collapses to a smaller diameter than current devices. The study pessary could become dislodged during ambulation or voiding, which may cause embarrassment.

16.0 Potential Benefits to Subjects

Subjects will not directly benefit from participation in this study.

17.0 Data Management and Confidentiality

Each subject who has signed a consent form and entered the study will be assigned a random study 3 digit number (001-999). Data related to the study will be handwritten on data collection forms (see attached document). The case report forms will not contain unique identifiers and will be referenced back to subjects only using the assigned study numbers. A separate key will be created linking the subjects with their random numbers. Once the key is created, it will remain in a locked cabinet which contains other study related documents (including, but not limited to, the protocol, instructions for use, all versions of the consent form, etc.). These documents will be maintained by study personnel through the trial and for 2 years after termination of the study and will only be accessible by study personnel.

Unidentifiable data from the case report forms may be collated in spread sheets for purposes of analysis. Such data will be exclusively stored and processed exclusively on password protected and encrypted computers.

Confidentiality protections include Dartmouth-Hitchcock Clinics confidentiality training for all employees and annual refresher seminars for all employees. Despite these protections, investigators will discuss with the eligible participants the potential for inadvertent disclosure of their data and ensure they are fully aware of these minimal, but possible risks. Breaches in confidentiality will be reported to Western IRB.

Reia, LLC is partially funded by the NIH. Reia is subject to potential auditing at any time by the NIH or the FDA. Reia, LLC may be required to release data from this study to these agencies if an audit were to be performed and this information were to be requested. The sponsor, monitors, auditors, the IRB, the Food and Drug Administration will be granted direct access to subjects' medical records to conduct and oversee the research. Excluding this circumstance, Reia, LLC will not intentionally release information to any individual, agency, or entity.

18.0 Provisions to Monitor the Data to Ensure the Safety of Subjects

Data Analysis and Data Monitoring

This is a non-randomized, non-blinded, early feasibility study involving a vaginal pessary. Given that this intervention is known to be safe and well-tolerated, there are 15 subjects with only one visit per subject, and the total time to recruit all subjects is anticipated to be 3 months, we do not believe a formal data safety monitoring committee is required. However, a data and safety monitoring plan will be in place. The data safety monitoring plan will focus on low intensity monitoring by the Data Safety Monitoring Team, comprised of the participating clinicians. The Data Safety Monitoring Team will meet every other week, or sooner if necessary, to review subject accrual, adherence to

PROTOCOL TITLE: *Early Feasibility Prospective Open Label Study to Assess the Function of a Novel Pessary for the Non-Surgical Management of Pelvic Organ Prolapse*

study protocol, and ensure prompt reporting of serious and adverse events to Western IRB and the study sponsor (Reia, LLC).

At each contact with the subject, the clinical investigator will seek information on adverse events by specific questioning and by examination. Information on all adverse events will be recorded for review by the Data Safety Monitoring Team. Moderate adverse events will be reviewed by the Data Safety Monitoring Team within one week. Serious adverse events, as defined by FDA criteria, will be reviewed by the Data Safety Monitoring Team within 24 hours and reported to Western IRB and the study sponsor (Reia, LLC). Careful monitoring of the recruitment, enrollment, study procedures, and adverse events will help protect the safety of the subjects and quality of the data.

Any unanticipated adverse device effects will be immediately evaluated by the sponsor, Reia, LLC. If it is determined that the adverse device effect presents an unreasonable risk to the subjects, the investigation will be terminated within 5 working days of making the determination and not more than 15 working days of first receiving notice.

In compliance with 21 CFR §812.46, if the sponsor, Reia, LLC, discovers that the study team is not complying with the signed agreement, the study protocol, applicable FDA regulations, or any conditions for approval of this IRB application, then Reia, LLC will either secure compliance or stop delivery of the device and terminate the investigator's participation. Additionally, Reia, LLC will require the remaining investigational devices be returned.

Protection Against Risks

Most risks for participating in this study are associated with discomfort in use of the study pessary, either with insertion, removal, or unintentional expulsion. Per the above protocol, the subject will be awake and unsedated for the complete encounter and will be able to communicate any discomfort experienced, and the subject's level of discomfort will be assessed at several points.

It is unlikely that an incidental finding will be discovered since the study population presents for similar care every 4 months. In the event there is a finding, the member of the clinical research team who has been providing treatment for the subject will follow through to provide appropriate care or make appropriate referrals.

Adverse events will be classified as Grade 1 or mild (easily tolerated by the subject no intervention necessary), Grade 2 or moderate (causing discomfort or interrupting usual activities), or Grade 3 or severe (causing considerable interference with usual activities, may be incapacitating, or may require hospitalization). Treatment of any adverse event, if indicated, will be coordinated by the member of the clinical study team who provides typical care for the study participant. Specific adverse events will be monitored as outlined in the data and safety monitoring plan described in the above section.

PROTOCOL TITLE: Early Feasibility Prospective Open Label Study to Assess the Function of a Novel Pessary for the Non-Surgical Management of Pelvic Organ Prolapse

Additionally, the clinical research team will report any adverse events (regardless of whether the event is serious or non-serious) which are *unexpected* and *related to the research procedures* within 5 working days to the study sponsor (Reia, LLC) and Western IRB. Grade 4 (life threating consequences requiring immediate intervention) and Grade 5 (death related to adverse event) terminate the study and will be reported to Western IRB and the study sponsor within 24 hours.

The subject will have the opportunity to stop the study at any point if desired. She will never leave the facility while using the study pessary and will, therefore, have immediate access to care if a problem arises. The subject will be given a copy of the consent form which lists the telephone numbers for the triage nurse of the principle investigator, as well as a 24-hour telephone number for the on-call physician if concerns arise after study participation.

No publication or public presentation about the research described above will reveal the subject's identity. Once data collected for this research study is no longer identifiable, the data may be used for other purposes. Protected health information will be handled as described in "13.0 Recruitment Methods" and "17.0 Data Management and Confidentiality."

